5. STUDY ENTRY AND WITHDRAWL

5.1 Required Preregistration Screening Tests and Procedures

The study-specific assessments are detailed in this section and outlined in the Study Calendar of Events. Screening assessments must be performed within 30 days prior to registration. Any results falling outside of the reference ranges may be repeated at the investigator's discretion. Visit procedures that were performed as standard of care prior to consent (without the specific intent to make the subject eligible for the trial), may count toward screening tests and eligibility if they are within the screening window.

A written, signed informed consent form (ICF) and a Health Insurance Portability and Accountability Act (HIPAA) authorization must be obtained before any study-specific assessments are initiated. A signed ICF copy will be given to the subject and a copy will be filed in the medical record. The original will be kept on file with the study records.

All WON sites under the purview of their local IRBs follow recruitment and consent processes approved by the local IRB of record. WON sites for which UW HS-IRB is serving as the IRB of record, will follow recruitment and consent process approved by UW HS-IRB. Documentation of both the informed consent process and that the process occurred prior to a subject's entry into a WON study is recorded in the subject's source documents.

All subjects who agree to participate and provide written informed consent and HIPAA authorization will be registered in OnCore®, the UWCCC and WON Cancer Center Clinical Trial Management System. The system is password protected and meets HIPAA requirements.

5.2 Registration Process

Patients must not start protocol treatment prior to registration.

Research personnel at WON sites who enter data into OnCore® must have completed human subjects training and Health Insurance Portability and Accountability Act (HIPAA) training.

At the time of registration, the following will be required and verified by (UWCCC):

- Subject eligibility
- Signed informed consent form
- Signed HIPAA authorization form

Refer to the Study Operations Manual for additional details regarding registration and eligibility verification.

5.3 Discontinuation of Study Treatment, Withdrawal, and Compliance

Discontinuation from the study treatment does not mean discontinuation from the study. Subject will be considered in follow-up, study procedures should still be completed as indicated by the study protocol, and AEs/SAEs will continue to be reported according to this protocol.

In the absence of treatment delays due to adverse events, study treatment/intervention may continue until:

- Disease progression.
- General or specific changes in the subject's condition renders the subject unacceptable for further treatment in the investigator's judgment.
- Intercurrent illness that prevents further treatment administration.
- Subject decides to withdraw from the study.
- The subject has significant noncompliance with the protocol (see below).
- Unacceptable adverse event(s) and/or dose level reduction beyond requirements as detailed in this protocol.
- Study stopping rules are met.

Subjects who sign the informed consent form, enroll, and receive the study intervention, but subsequently withdraw, or are withdrawn or discontinued from the study will not be replaced.

5.3.1 Consent Withdrawal

A subject may decide to withdraw from the study at any time by informing the study principal investigator or the site study team.

If a subject intends on withdrawing consent, staff should confirm which of the following options the subject chooses and document the discussion:

- Full consent withdrawal with no study follow-up.
- Selective consent withdrawal from interventional portion of the study but agrees to continued follow-up of associated clinical outcome information.

5.3.2 Investigator-Initiated Withdrawal

The investigator will withdraw a subject whenever continued participation is no longer in the subject's best interests. Reasons for withdrawing a subject include, but are not limited to, disease progression, the occurrence of an adverse event or a concurrent illness, a subject's request to end participation, a subject's noncompliance or simply significant uncertainty on the part of the investigator that continued participation is prudent. The reason for study withdrawal and the date the subject was removed from the study must be documented.

Subjects withdrawn from study treatment will be asked to return for a 30-day follow-up visit, and future appointments are at the discretion of the treating provider, but not required beyond 30 days per the study guidelines.

Withdrawal Documentation Procedure: The reason for study withdrawal and the date the subject was removed from the study must be documented in the case report form.

5.4 Lost to Follow-Up

The following actions must be taken if a participant fails to return to the clinic for a required study visit and/or is unable to be reached for follow-up:

- The investigator or designee must make every effort to regain contact and/or reschedule a missed visit with the subject.
- A subject is deemed lost to follow-up if his/her status cannot be obtained after all of the following occurs at two consecutive scheduled protocol calendar time points:
 - Three telephone calls (at least one day apart) from the study team are unanswered,
AND
 - A letter to the subject's last known mailing address goes unanswered,
AND
 - These contact attempts must be documented in the subject's medical record or study file.
- Update OnCore® (follow-up tab and eCRF) when a subject is officially considered lost to follow-up.
- If a subject is considered lost to follow-up, but subsequently contacts the study team, the subject should be considered in follow-up again.

5.5 End of Study Definition

A subject is considered to have completed the study if he or she completes all phases of the study, including the last visit or the last scheduled procedure shown in the calendar of events or is discontinued.

5.6 Study Discontinuation and Closure

This study may be temporarily suspended or prematurely terminated if there is sufficient reasonable cause (as determined by the study PI, DSMC, sponsor, and/or IRB). Written notification, documenting the reason for study suspension or termination, will be provided by the suspending or terminating party to study participants, investigator, funding agency, the Investigational New Drug (IND) sponsor and regulatory authorities. If the study is prematurely terminated or suspended, the principal investigator (PI) will promptly inform the Institutional Review Board (IRB), and the sponsor and will provide the reason(s) for the termination or suspension. Study participants will be contacted, as applicable, and be informed of changes.

6 TREATMENT PLAN

6.1 Investigational Agent Administration

All patients will receive onapristone 50 mg by mouth twice (BID) daily and fulvestrant (500 mg) intramuscular injection on cycle1 days 1 and 15, then, 500 mg once monthly until progression beginning with cycle 2 day 1. There will be no breaks between dosing cycles. A complete cycle of treatment is defined as 28 days. All dosages prescribed and dispensed to the subject and all dose changes during the study must be recorded on the CRF.

Treatment or visit delays for public holidays or weather conditions do not constitute a protocol violation.

6.1.1 Fulvestrant

Fulvestrant dose of 500 mg (or two injections of 250 mg each) will be used. For information on fulvestrant and management of related AEs refer to the Faslodex® prescribing information. Fulvestrant will be procured locally according to local practice and regulation. Fulvestrant (500 mg) intramuscular injection will be administered on days 1, 15 (cycle 1), then two weeks later (cycle 2, day1), then once every 28 days thereafter.

6.1.2 Onapristone

The dose of onapristone will be 50 mg twice daily (BID). Context Therapeutics or its designee will provide onapristone as coated tablets of 20 mg and 10 mg strength to allow for dose modification for management of adverse events in bottles of 60 tablets each. The storage conditions for the onapristone will be described on the medication label. Medication labels will comply with the legal requirements in the United States.

The investigator should instruct the subject to take the study drugs as per protocol and drug accountability must be performed on a regular basis. Subjects will be instructed to return unused study drugs and empty containers to the site at the end of each cycle. Subjects will be given a pill diary to track onapristone dosing and will be instructed to return the diary at their next clinic visit along with all pill bottles (including empty bottles). Site personnel will review the diary with each subject to evaluate adherence to the dosing schedule.

All dosages prescribed and dispensed to the subject and all dose changes during the study must be recorded on the CRF. The following general guidelines should be followed for onapristone administration:

Subjects should be instructed to take onapristone twice daily every 12 hours, and the dosing is independent of food intake. For any missed doses, subjects are allowed a 4 hour window, and any dose missed by more than 4 hours should not be taken (at least 8 hours between doses). For example, if the first dose is taken at 6 am, the evening dose will be at 6 pm. If the morning dose is missed, they can take onapristone up until 10 am and skipped doses aren't allowed after 10 am. If the subject ends up taking the morning dose at 10 am (instead of 6 am), the subject can take the evening dose at 6 pm as originally planned, and get back to the regular schedule starting the next day.

Onapristone should be taken with a glass of water. Subjects should swallow the tablet as a whole and not chew or crush them. If vomiting occurs during the course of treatment, no redosing of the subject is allowed before the next scheduled dose. The occurrence and frequency of any vomiting during a treatment cycle must be noted in the adverse events section of the CRF.

6.1.3 ^{18}F -FFNP

^{18}F -FFNP is an investigational radiopharmaceutical used with PET/CT for visualizing PR-rich target tissues and quantifying available PR-binding sites. It is given in a tracer dose amount for imaging purposes. The compound is not a therapeutic agent.

If funding is secured and workflows are in place, the optional PET/CT scans will be performed at UWCCC and may also be performed at other WON sites participating in the Wisconsin Oncology Network of Imaging eXcellence (WONIX).

The optional PET/CT will be completed at least 24 hours prior to C1D1 (no more than 7 days prior) and repeated 7 to 14 days after C1D1. Prior to arrival, the subject should be well-hydrated and does not need to be fasting.

Upon arrival, the subject's height, weight, and vital signs (blood pressure, heart rate, respiratory rate, and temperature) should be recorded. The subject will have an intravenous line placed (e.g., 20 g, antecubital vein), typically in the arm opposite to the side of primary breast cancer or side of prior axillary lymph node surgery.

The dose of the investigational imaging agent, ¹⁸F-FFNP, is approximately 7 mCi (259 MBq), IV slow infusion over approximately two minutes followed by saline flush. The injection site will be inspected by the technologist to assess for any possible infiltration.

Vital signs (blood pressure, heart and respiratory rate, and temperature) will be taken after injection. The subject will wait approximately 60 minutes to allow for biodistribution and tumor uptake of the radiopharmaceutical prior to imaging. The subject should void immediately prior (five to 10 minutes) to image acquisition. Vital signs (blood pressure, heart and respiratory rate, and temperature) will be taken after the imaging acquisition is complete. Subjects will be contacted by site personnel to evaluate for adverse events occurring in the 24 hours following the PET/CT scan. This can be done via a telephone call at least 24 hours, but not more than 72 hours after the completion of the PET/CT scan.

Supportive Care

During the study period, blood transfusions, bone-modifying agents for bone metastases, radiation, and other supportive care measures (i.e., growth factor support, physical therapy, lymphedema therapy, acupuncture) are allowed for symptom control.

Patients are allowed to continue the study treatment during radiation if agreeable to the treating provider. New symptoms, such as pain, are not considered disease progression, and patients are allowed to be on the study treatment unless/until there is a clear disease progression on imaging.

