7. Subjects who chose to undergo the optional ¹⁸F-FFNP PET/CT for PR imaging will undergo a baseline scan at least 24 hours prior to starting treatment (no more than 7 days prior) and a follow-up scan seven to 14 days after starting treatment.
8. Fulvestrant will be given days 1 and 15 in cycle 1. The C2D1 dose should be given two weeks after C1D15 dose. Fulvestrant dosing will be every 28 days beginning with C2D1.
9. Imaging scans per section 10.1; imaging frequency (with windows) per section 10.2. Imaging at end of treatment visit not required if completed within the past 6 weeks. Skin photography required if skin lesions are present and amenable to photography.
10. If blood for correlative studies was not collected at the end of treatment visit, it should be collected at the safety visit and prior to starting any new treatment. Please refer to section 10.5.1 and 10.5.2.
11. If a research sample was drawn at Cycle 3 Day 1 and subject stopped treatment at that time, a third sample is not required.

LIST OF ABBREVIATIONS

ABCAE	advanced breast cancer adverse event
AE	adverse event
ALP	alkaline phosphatase
ALT	alanine aminotransferase
ANC	absolute neutrophil count
AST	aspartate aminotransferase
AUC	area under the curve
BUN	blood urea nitrogen
CBC	complete blood cell (count)
CDK	cyclin-dependent kinases
CQ	chloroquine
CR	complete response
CRC	clinical research coordinator
CRF	case report form
CSF	cerebral spinal fluid
CT	computed tomography
CTCAE	Common Terminology Criteria for Adverse Events
CTL	cytotoxic T cell
CTO	Clinical Trials Office
DFS	disease-free survival
DLT	dose-limiting toxicity
DSMC	Data and Safety Monitoring Committee
DSMP	data and safety monitoring plan
ER	estrogen receptor
¹⁸ F-FFNP	¹⁸ F-fluorofuranyl norprogesterone
FDA	Food and Drug Administration
GCP	good clinical practice
HCQ	hydroxychloroquine
HCT	hematocrit
HER 2	human epidermal growth factor receptor 2
HGB	hemoglobin
IP	investigational product
IRB	Institutional Review Board
LDH	lactate dehydrogenase

LMWE	low molecule weight isoforms of cyclin E
MCWCC	Medical College of Wisconsin Cancer Center
MTD	maximum-tolerated dose
NCI	National Cancer Institute
ORR	overall response rate
PBMC	peripheral blood mononuclear cells
PD	disease progression
PET	positron emission tomography
PDAC	pancreatic ductal adenocarcinoma
PK	pharmacokinetics
PR	partial response
PgR	progesterone receptor
Rb	retinoblastoma
RBC	red blood cell (Count)
ROS	reactive oxygen species
SAE	serious adverse event

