1.4.1.7 Pharmacokinetics of Onapristone

In the phase I trial(16), plasma concentrations of ONA, mono-demethylated ONA (M1) and other metabolites in plasma and urine were analyzed with a validated ultra-performance liquid chromatography with tandem mass spectrometry detection (UPLC-MS/MS) assay. Results showed that ONA AUC and Cmax were dose-proportional across dose levels, with high correlation coefficients (R2 values are 0.76 and 0.97, respectively, see Figures 5 and 6). Average Tmax was 3.01 hours (2.71–3.2) vs 1.84 hours for ER versus IR formulations, respectively, and concentrations of drug were sustained longer with a 60% (± 20) relative bioavailability for ER vs IR formulation. Steady state for the ER formulation was attained before day 8, and the mean ONA minimum concentrations at steady state were up to five times those obtained at day 1; day 8 through levels were similar to day 1 for IR. There was no evidence of ONA accumulation at day 57. The observed mean t1/2 for the ER formulation was approximately 18.01 hours (range, 13.9 to 37), consistent with steady state achievement before day 8. ONA plasma concentration versus time curves suggest biphasic elimination.

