10.5.3 Functional Imaging

18F-FFNP PET/CT Imaging Protocol

For this study, PR functional imaging using ¹⁸F-FFNP PET/CT will be performed for up to 12 subjects. Quantitative molecular imaging with ¹⁸F-FFNP PET/CT before and seven to 14 days after starting therapy may be useful to confirm optimal dosing of onapristone to block PR binding to ¹⁸F-FFNP in patients with extrahepatic metastases. Incomplete receptor blockade, indicating suboptimal dosing, may be associated with earlier disease progression. The change in tumor ¹⁸F-FFNP uptake after starting therapy will be evaluated as an estimate of PR binding availability. Tumor ¹⁸F-FFNP uptake parameters (SUV_{max}, SUV_{mean}, SUV_{peak}, tumor-to-normal tissue uptake ratio, functional tumor volume, and total lesion uptake) will be measured before and after starting therapy.

PET/CT scanners at UW-Madison are qualified by the American College of Radiology (ACR) Imaging Core Laboratory and have been approved for use in current ECOG/ACRIN trials. The scanner routinely will be assessed for quantitative integrity and stability by being tested using various imaging protocols on a standard phantom. For SUV measurement, this includes a comparison against a dose calibrator to ensure accuracy. A daily QC check will be performed at the beginning of the day, including PET/CT scanner and dose calibrator, in accordance with the manufacturer recommendations. If any of the QC results are outside of the manufacturer's guidelines, the study will be rescheduled, and the problem rectified before scanning any subjects. ¹⁸F-FFNP PET/CTs not completed within the protocol-specified windows due to QC results will not be considered a protocol deviation.

A PET Imaging Protocol Manual specific to this clinical trial will be prepared for the research study coordinators and nuclear medicine technologists at UW-Madison. Subjects do not need to be fasting for ¹⁸F-FFNP PET/CT imaging, but will be encouraged to be well hydrated. The subject's weight will be measured the day of imaging. ¹⁸F-FFNP will be synthesized according to cGMP requirements and processed for QA/QC by the UW Radiopharmaceutical Production Facility. For each research imaging session, subjects will receive ¹⁸F-FFNP, approximately 7 mCi (259 MBq), IV slow infusion over approximately two minutes followed by saline flush, once administered in the PET imaging suite.

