10.5.7 Definition of 18F-FFNP Blockade

The same five target lesions will be analyzed for quantitative 18F-FFNP uptake on the second 18F-FFNP PET/CT examination as on the initial scan. If the SUVmax for all five lesions have decreased by > 75% or all five lesions have SUVmax < 1.5 on the second scan, then these subjects will be prospectively defined as having complete 18F-FFNP blockade. If the SUVmax for any of the five lesions has not decreased by > 75% or if any new lesions arise with SUVmax ≥ 1.5 , then these subjects will be defined as having incomplete 18F-FFNP blockade. Changes in radiotracer uptake in normal organs with expected 18F-FFNP uptake (pituitary gland and uterus) will also be measured as an internal reference.

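### The second 18F-FFNP scan and the blockade definition take no account of time since the last onapristone dose or of missed or held doses, so non-receipt of drug can be read as suboptimal dosing

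*Combined protocol and SAP*

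**What the plan says.** **Timing of scan 2.** Section 6.1.3 places the first scan before treatment, "and repeated 7 to 14 days after C1D1". Footnote 7 of the study calendar likewise asks for "a follow-up scan seven to 14 days after starting treatment". Section 10.5.3 gives the same range of days. The imaging sections fix the tracer activity, an uptake time of about 60 minutes, the scanner and the reconstruction method. They do not fix hours since the last onapristone dose.

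**Classification.** Section 10.5.7 has two routes to complete blockade: "If the SUVmax for all five lesions have decreased by > 75% or all five lesions have SUVmax < 1.5 on the second scan". The opposite class applies "If the SUVmax for any of the five lesions has not decreased by > 75" per cent, or when a new lesion appears with SUVmax of 1.5 or more. Neither sentence carries a dose-time or adherence condition.

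**Interpretation.** Section 10.5.3 says the paired scans may help confirm that the onapristone dose blocks the receptor, and adds: "Incomplete receptor blockade, indicating suboptimal dosing, may be associated with earlier disease progression".

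**Dosing.** Under section 6.1.2 subjects "take onapristone twice daily every 12 hours", and "any dose missed by more than 4 hours should not be taken". Table 5 orders interruptions for several adverse events, for example grade 2 ALT or AST elevation. A pill diary is kept, but the study calendar marks drug adherence at day 1 of each cycle and at the end of treatment, not at the scan.

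**The concern.** The sub-study uses the change in uptake to judge whether the dose is adequate. That inference needs the drug to have been taken as planned before the scan. The plan neither ensures this nor records it with the scan, and it does not say how to class a scan done after a skipped dose or during a hold. One lesion short of the 75% cut is enough for the incomplete class, and at most 12 subjects are imaged. A small number of scans affected by missed drug could thus be reported as evidence that the dose is too low. If the time of the last dose is not noted at the scan, it may not be recoverable later to the hour.

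**Working it through.** **Inputs from section 1.4.1.7.** Tmax for the extended-release tablet is 3.01 h. For the half-life: "The observed mean t1/2 for the ER formulation was approximately 18.01 hours (range, 13.9 to 37" hours). Steady state is reached before day 8, and steady-state minimum concentrations are up to five times those of day 1. The dosing interval is 12 h (section 6.1.2).

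**Assumptions not in the documents.** One-compartment oral model; fractional fall in SUVmax = C/(C + IC50), following plasma level without delay; the whole fall due to onapristone; only the >75% route applied.

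**Step 1: reproduce the protocol's own figures.** Accumulation = 1/(1 − 2^(−12/t½)) gives 2.22, 2.70 and 4.97 at half-lives of 13.9, 18.01 and 37 h. The top value matches the stated five-fold. The fraction of steady state at 168 h, 1 − 2^(−168/t½), is 99.98%, 99.8% and 95.7%, in line with steady state before day 8. The scan window therefore lies at or near steady state.

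**Step 2: level relative to peak.** Let k = ln2/t½. Solving ln(ka/k)/(ka − k) = 3.01 gives ka = 1.17 per hour at 18.01 h (1.07 at 13.9 h, 1.47 at 37 h). At steady state C(t) is proportional to e^(−kt)/(1 − e^(−12k)) − e^(−ka·t)/(1 − e^(−12ka)). Let f be C(t) divided by the peak. By 24 h the absorption term is negligible, so f(48) = f(24) × 2^(−24/t½). This is 0.446 × 0.397 = 0.177 at 18.01 h, 0.354 × 0.302 = 0.107 at 13.9 h, and 0.670 × 0.638 = 0.427 at 37 h.

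**Step 3: who changes class.** With x = C/IC50 the fall is x/(1 + x), and a 75% fall means x = 3. A subject above 75% at peak drops to 75% or less if the fall at peak is no more than 3/(3 + f).

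| Time since last dose | f at 18.01 h (range over 13.9–37 h) | Peak falls that change class: 75% up to |
|---|---|---|
| 12 h, no missed dose | 0.71 (0.64–0.84) | 80.9% (78.2–82.3) |
| 16 h, dose 4 h late | 0.61 (0.53–0.78) | 83.2% (79.4–85.0) |
| 24 h, one skipped dose | 0.45 (0.35–0.67) | 87.1% (81.8–89.4) |
| 48 h, during a hold | 0.18 (0.11–0.43) | 94.4% (87.5–96.6) |

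Examples at 18.01 h: a peak fall of 80% becomes 74% at trough and 64% after a skipped dose. One of 85% becomes 80% and 72%. One of 90% becomes 86% and 80%, and does not change class in either case.

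**Step 4: what a fixed window would do.** If all scans fell within a 2 h band after the peak, the spread in level would be 1 − 2^(−2/18.01), about 7%. Without a rule it is about 29% (1 − 0.71) with no late or missed dose, and about 55% (1 − 0.45) if one dose may have been skipped.

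**The case against.** - **Clock time alone matters little.** With no missed dose, only subjects within about 6 points above the cut (3 to 7 over the half-life range) change class. A reader might infer that any subject's class is arbitrary, depending on the hour of the scan; the documents' own half-life does not support that. This stands. The case rests mainly on missed and held doses.
- **A failure at trough may be real.** If blockade is lost before the next scheduled dose, that bears on the dose question. This also stands: a trough scan in an adherent subject is not an error, and the fault is that the hour is neither fixed nor recorded.
- **The model is assumed.** No concentration–occupancy relation is given. Fulvestrant starts on the same day and peaks at about day 5 (section 1.3.1), and section 1.2.2 describes PR as a downstream target of ER. Any part of the fall due to fulvestrant would not depend on onapristone dose time. Against this, section 1.4.1.7 suggests biphasic elimination, so the early decline could be steeper than modelled.
- **The SUVmax <1.5 route can protect low-uptake lesions.** A 74% fall still ends below 1.5 if baseline SUVmax is under about 5.7 (1.5/0.261); for a 64% fall the limit is about 4.2 (1.5/0.359). No baseline values are given. The two sentences of section 10.5.7 overlap for such a subject, which is a separate matter.
- **Section 6.1.2 does not approve 24 h gaps.** A reader might infer that it does. It asks for 12-hourly dosing, and the 4-hour rule only says what to do once a dose is missed. The diary and the CRF record of dose changes capture part of the history, but nothing links them to the scan or the classification.
- **The PET Imaging Protocol Manual** still to be prepared may set the appointment hour. The definition and its interpretation are in the protocol, however, so the handling of missed doses belongs there.

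**Conclusion.** The omission is clear from the text and needs no model: scan 2 is timed by day only, the blockade definition ignores dose history, and incomplete blockade is read as suboptimal dosing. A scan after a skipped dose or during a Table 5 interruption can be misread in that way. The size is illustrative: an upper limit of about 81% at trough, 87% after one skipped dose and 94% at 48 h, under the assumptions listed and for the 75% cut only. The number of subjects affected cannot be estimated.

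A reader might infer that the trial's main conclusion is at risk. It is not. The scans are optional, depend on funding, cover at most 12 subjects, do not appear in the table of objectives and endpoints, and have no decision rule in section 9.2. The point is minor but worth correcting.

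**What to change.** **Sections 6.1.3 and 10.5.3.** Book scan 2 in one prespecified window of hours after an onapristone dose, the same for all subjects. Record with the scan the time of the last dose and any doses missed or held in the previous 3 days (72 h, about four half-lives at 18 h and about two at 37 h). If a missed or held dose is known beforehand, move the appointment within the day 7–14 window.

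**Section 10.5.7.** Report scans preceded by a missed or held dose separately, do not read them as suboptimal dosing, and give the blockade result with and without them. This also covers a hold that outlasts the window.

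Do not add a third scan once scan 2 has been done: section 7.5.3 puts each PET/CT at about 10 mSv, and another tracer production would be needed. No dosing rule has to change.

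**Cost.** Slightly less flexible booking, a few extra CRF fields, and possibly fewer classifiable subjects.
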